Gender differences in prevention strategies and therapeutic adherence after acute myocardial infarction

GENAMI PREVENTION

Study protocol

Principal Investigator Contact Information

[name], PhD

Área de Investigación Cardiovascular. Instituto de Investigación i+12

Servicio de Cardiología. Hospital Universitario 12 de Octubre, Madrid

Centro Nacional de Investigación Cardiovasculares (CNIC)

SUMMARY

Background and objectives. Women with acute myocardial infarction (AMI) are less likely to receive acute treatments according to guidelines recommendations, often present worse short- and long-term outcomes, and are less likely to receive secondary prevention therapies. However, comparisons have been hampered by several differences in the epidemiology, pathophysiology and presentation of AMI between men and women, including age, comorbidities, pathophysiology, and AMI types.

While several studies have been dedicated to understand and reduce the gender gap in acute care, the role of gender on compliance with secondary prevention recommendations (pharmacological and non-pharmacological), and the factors associated with non-compliance in women are largely unknown.

The aims of the study is to compare between a cohort of women who have suffered an AMI and a comparable cohort of men: 1) the proportion of 6- and 12-month adherence to the secondary cardiovascular prevention recommendations, 2) the proportion of patients with adequate control of risk factors, 3) the incidence of clinical outcomes, and 4) to study the factors associated with lower adherence (including biological, disease-related, psychosocial, and gender-related).

Design. Prospective, matched cohort study of patients hospitalized for type 1 acute myocardial infarction with significant coronary artery disease. The reference cohort will be composed of 500 women and the comparison group of 500 men with a 1:1 matching for age (± 2 years) and ECG (STEMI/NSTEMI), with 1-year follow-up assessing adherence with pharmacological and non-pharmacological secondary prevention recommendations, risk factor control and clinical outcomes.

End-points. Primary end-point: composite outcome of adherence to all secondary CV prevention recommendations 12 months after discharge, including pharmacological therapies, diet, physical activity and participation in cardiac rehabilitation programs. Secondary end-points: adherence to all secondary CV prevention recommendations at 6 months, percentage of patients achieving optimal control of all individual CV risk factors, composite clinical endpoint at 12 months: all-cause death, all-cause rehospitalization, and all-cause emergency department visits, among others.

Statistical analysis. A logistic regression models will be used to evaluate differences in the primary outcome between women and men, as well as in other outcomes. All subjects will be assumed to have a fixed follow-up (12 ± 1 month). Multivariate adjusted models will be used to address any potential confounding in the associations between sex and each of the outcomes. Covariates will be selected based on their pre-defined clinical value and the unbalances observed across groups in the univariate analyses.

Sponsor: Sociedad Española de Cardiología

Funding: ORGANON (Unrestricted grant)

Principal Investigator: [name], PhD

Executive Committee: [name], PhD; [name] [name], PhD, [name] [name], PhD, [name], PhD; [name], PhD

Scientific Committee: [name], PhD; [name] [name], PhD, [name] [name], PhD; [name] [name], PhD, [name], PhD; [name], PhD; [name] [name], PhD; [name] [name], PhD; [name] [name], PhD;

Clinical sites (25)

	C. Autónoma	Hospital	Población
1	Andalucía	Hospital Universitario Virgen Macarena	Sevilla
2	Andalucía	Hospital Universitario Virgen de la Victoria	Málaga
3	Aragón	Hospital Universitario Lozano Blesa	Zaragoza
4	Asturias	Hospital Universitario Central de Asturias	Oviedo
5	Baleares	Hospital Universitari Son Espases	Palma de Mallorca
6	C. La Mancha	Complejo Hospitalario de Toledo	Toledo
7	C. La Mancha	Complejo Hospitalario Universitario de Albacete	Albacete
8	C. León	Hospital Clínico Universitario de Salamanca	Salamanca
9	C. León	Complejo Asistencial Universitario de León	León
10	C. Madrid	Hospital Universitario Fundación Alcorcón	Alcorcón
11	C. Madrid	Hospital Universitario 12 de Octubre	Madrid
12	C. Valenciana	Hospital General Universitario de Alicante	Alicante
13	C. Valenciana	Hospital Clínico Universitario de Valencia	Valencia
14	Canarias	Hospital Universitario de Gran Canaria [name] (*)	Las Palmas de Gran Canaria

1. RATIONALE AND BACKGROUND

Coronary artery disease (CAD) is the leading cause of death worldwide, both in women and men,¹ mostly driven by acute coronary syndromes. Actually, CAD kills twice as many women as breast cancer.² In recent years there has been a decrease in the fatality rate due to CAD³ of 31.8% (from 2006 to 2016), standing at 132.3 in men and 67.9 in women, of white race, per 100,000 inhabitants (146.5 and 85.4 for men and women, of African American race, respectively).⁴ Part of this phenomenon is due to a decrease in recent years in the incidence of ST-segment elevation acute myocardial infarction (STEMI), a slight increase in the incidence of non-ST-segment elevation acute myocardial infarction (NSTEMI) and a decrease in in-hospital mortality.⁵⁻⁸ However, these data are controversial, since the annual incidence of hospitalizations for AMI has increased in young people, with the greatest increase observed in young women. Also trends in mortality have changed, with increasing CAD mortality among women and higher in-hospital mortality in young women (<45 years).^{9,10} Women with AMI are undertreated and also have a greater burden of comorbidities.^{11,12} Likewise, the number of hospitalizations for AMI, as well as the risk of in-hospital mortality, has been decreasing in recent years (although in-hospital mortality in women has increased slightly).¹³ One other factor that explains the decrease in mortality after an AMI is the development and implementation of effective evidence-based therapies, such as coronary revascularization and pharmacological treatments. These treatments are started in the acute hospitalization phase and are continued during follow-up (secondary prevention).¹⁴ These facts should persuade us to conduct further studies, especially in young women, to try to explain these effects.

The role of biology and gender in the pathophysiology and outcomes of AMI

There are notable differences in the susceptibility and pathophysiological mechanisms of AMI between men and women, some biologically-based but others due to environmental factors, among which, gender-specific conditions have gained interest in recent years. Men have a greater predisposition to atherothrombotic (type 1) AMI, usually presenting at younger ages. In contrast, although type 1 is the most common form of presentation in women, they

present more frequently other mechanisms of AMI (i.e. type 2 myocardial infarctions caused by spontaneous coronary artery dissection, or AMI with non-obstructive coronary artery disease —MINOCA—, i.e. coronary vasospasm or microvascular dysfunction, especially in the younger age group).¹⁵

Most medical treatments that demonstrated clinical benefits in AMI did so mainly in patients with type 1 AMI (antiplatelet drugs, lipid-lowering therapies, beta-blockers...).

Risk factors for atherosclerotic CAD can be classified in four major groups:

- Traditional cardiovascular risk factors. Cardiovascular risk factors are underreported in women who come to the Primary Care consultation.^{16,17} This lack of diagnosis prevents specific preventive actions. Another noteworthy aspect is that while in men there has been a decrease in unhealthy lifestyle habits such as smoking, in women, especially in the younger group, it has remained stable or may even have increased.^{3,18} Obesity and sedentary lifestyle are more frequent in women. Notably, the impact of metabolic risk factors such as diabetes could confer a higher cardiovascular risk in women than in men.¹⁸
 - o Non-modifiable biological risk factors: age, sex, ethnic background, familiar history of cardiovascular disease.
 - o Modifiable risk factors: hypertension, diabetes, dyslipidemia, smoking, obesity.
- Non-traditional risk factors: obstructive sleep apnea syndrome and chronic kidney disease.
- Sex-specific risk factors.^{2,19–25} A number of clinical conditions unique to women that have been identified to be associated with increased risk of cardiovascular disease. Reproductive factors include early menarche, early menopause, history of miscarriages, reproductive treatments, polycystic ovary syndrome (which is closely related to metabolic syndrome and insulin resistance), gestational diabetes, number of pregnancies, breastfeeding and lactation duration, hysterectomy, hormone replacement therapy, use of hormonal contraceptives, history of pre-eclampsia, eclampsia, or pregnancy-associated hypertension ². Female protection against CVD is associated with sex hormone levels as the incidence and severity of CVD increases in postmenopausal

women²⁶ and the prevalence of CAD is greater in young women who had an oophorectomy compared to those with intact ovaries.²⁷ Taken together, this data has sparked much investigation into the potential of female sex hormones in conferring cardioprotection. The mechanisms that explain the association between these factors and the increase in cardiovascular risk are complex, but could be related to greater adiposity in patients who present them (i.e. polycystic ovary syndrome, early menarche), proinflammatory factors or endothelial dysfunction, among others.²³

- Socio-economic factors: Social support acts as a protective element that reduces the impact of negative life events in people's lives.²⁸ Therefore, it is considered that poor social support is associated with a 1.5 to 2-fold increase in the risk of CVD, both in healthy people and in those with heart disease.²⁸ Low socioeconomic status is associated with increased risk of cardiovascular events, including AMI and poorer survival^{29,30}. The impact of material deprivation and level of socioeconomic resources is even greater in women than in men.³¹ For women, living in a deprived neighborhood may affect coronary health in a greater extent than men, especially in the younger stratum.³²
- Psycho-social risk factors.³³ Increasing importance is given to factors such as chronic stress, anxiety disorders, depression, personality factors, economic status, sleep disorders, social isolation or childhood trauma. Depression, anxiety, anger and stress (acute, chronic) are factors that increase cardiovascular risk.³⁴ It is considered that there is a dose-response relationship between depression and cardiovascular events, and therefore a more severe depression also increases cardiovascular risk.³⁵ Anxiety is related to an increase in cardiac mortality, especially in patients with a more severe cardiovascular disease. The influence of stress on cardiovascular risk depends on the presence of acute triggers, and chronic stress.³⁶ Acute stress affects cardiovascular physiology, increasing the risk of arrhythmias, myocardial ischemia, and may precipitate an acute myocardial infarction.³⁷ Chronic stress, however, seems to influence cardiovascular disease through chronic physiological disturbances, and is linked, among others, to work stress, marital

problems, long-term caregiving to people in a situation of dependency, aspects related to the neighborhood or the economic status.^{33,38} Work stress under burdensome domestic work has been strongly associated with depression in women and men³⁹ but there are differences in the levels of work overload reported between genders. Women reported higher levels of work overload, stress and conflict than men, which increased significantly with the number of children at home. The various stress indices reached a peak between the ages of 35 and 39.⁴⁰ The role of social, psychological and cultural factors has not been fully studied. Psychosocial factors have a greater impact on the outcomes of women who present with an AMI, especially in the younger age stratum, as they have high rates of poverty, social isolation, history of sexual abuse or childhood trauma and are often from minority groups.^{41,42} Depression is present in more than half of women aged <50 years who present with an AMI, and is associated with worse outcomes.^{43,44} The role of specific gender issues in the outcome of AMI has been seldom studied.^{45,46}

Gender differences in acute myocardial infarction presentation and management

Women with AMI often show longer delays to diagnosis, reperfusion therapy, and a higher risk of complications, such as bleeding, cardiogenic shock or mechanical complications.⁴⁷⁻⁵⁰ This worse prognosis has traditionally been attributed to their higher risk profile, with older age and more comorbidities.⁵¹

Women with AMI are less likely to receive timely reperfusion, other acute treatments, secondary prevention therapies or be referred to cardiac rehabilitation.^{52,53,54,55,56} There are sex-related disparities still observed today in the care of patients with infarction that disadvantage women and that extend to three key moments: ACS diagnosis, acute treatments (including DAPT at arrival and reperfusion therapy) and secondary prevention treatments (anti-platelets, statins, renin-angiotensin system inhibitors).^{57,58} Women are less commonly prescribed cardiac rehabilitation after ACS, and are particularly unlikely to participate in cardiac rehabilitation programs.^{59,60} As cardiac rehabilitation has

also shown benefit in women after an ACS, an effort is needed to increase utilization among women.

However, most comparisons between women and men with AMI are hampered by the major differences in the epidemiology and pathophysiology of AMI,¹³ including the older age of women, their greater comorbidity (particularly, renal disease),¹¹ increased risk of adverse effects with therapies (i.e. bleeding)⁴⁹ and the different proportion of different AMI types (i.e. women presenting more often with type-2 AMI or with non-obstructive coronary artery disease),^{15,55,61} which has therapeutic and prognostic implications. These differences need to be accounted for to improve the accuracy of comparisons and define more clearly the role of sex and gender on the management and outcomes of AMI.⁴⁶

Gender and determinants of adherence to evidence-based therapies after AMI

Age, gender, the presence of comorbidities and polypharmacy are factors that predict adherence to secondary prevention therapies⁶². Women with AMI have been found to have differences in adherence compared with men, with lower adherence to P2Y₁₂ inhibitors (i.e. clopidogrel)⁶³ or a 10% greater probability of non-adherence to statins.⁶⁴ In a study with 148,654 patients with AMI, who had received secondary prevention measures in accordance with the clinical guidelines (loading dose of antiplatelets and chronic doses of aspirin, beta-blockers and ACE inhibitors in patients with AMI and reduced left ventricular ejection fraction, lipid-lowering drugs and medical advice smoking cessation) female gender was associated with poorer adherence on all measures⁶⁵. However, a recent meta-analysis showed a lower adherence to lipid-lowering drugs (OR = 0.87, 95% CI 0.82-0.92) with no differences in the other three major pharmacological groups of secondary prevention (ACE inhibitors/ARA-II, beta-blockers and antiplatelets) in women post-MI,⁶⁶ but the role of the differences in age and comorbidities in these results is unknown. Regarding the adherence to non-pharmacological secondary prevention measures, registries and observational studies have observed that men are less likely to achieve blood pressure goals than women.⁶⁷ The results of the EUROASPIRE V survey also reveal that women change their healthy food habits in compliance with the recommendations, more frequently than men do.⁶⁸

With the increasing awareness of sex disparities in cardiac care in the last years, it is possible that the sex-related differences in the prescription of secondary prevention therapies have improved. However, in the last two years, due to the COVID-19 pandemic, social disparities have increased and this may have had an unfavorable impact on women's health, increasing the gender gap. The reasons for these differences are not well known and should be explored in order to develop interventions to improve effective secondary prevention strategies tailored for women, and their outcomes.

2. HIPOTHESIS

We have the following three alternative hypotheses.

Compared with men:

- the adherence to secondary prevention strategies after AMI is lower in women, regardless of their baseline differences.
- the control of CV risk factors after AMI is poorer in women.
- The incidence of clinical outcomes and/or use of healthcare resources after AMI is higher in women.

The null hypothesis for each of the previous statements is that there is no difference between men and women for each of the outcomes. The main rationale for our alternative hypotheses is based on gender-related factors rather than on biological differences.

In addition, we hypothesize that there are gender-related factors associated with (non-) adherence to secondary prevention recommendations in women.

3. OBJECTIVES

General objective. To evaluate if there are differences in the level of adherence to recommended secondary prevention therapies (pharmacological and non-pharmacological) between women and men surviving a type 1 AMI (with obstructive CAD), its potential consequences, and the potential factors related to that difference, if present.

Specific objectives. To compare between women and men:

- 1) The adherence to recommended secondary prevention therapies at 6 months and 12 months measured as the
 - 1a. Proportion of patients adherent to all recommended pharmacological secondary prevention therapies at 6 and 12 months
 - 1b. Proportion of patients adherent to all recommended non-pharmacological secondary prevention therapies at 6 and 12 months
- 2) The relationship of the adherence with control of risk factors, clinical outcomes, and use of healthcare resources
 - 2a. The proportion of patients with optimal control of all cardiovascular risk factors at 6 and 12 months
 - 2b. The incidence of clinical outcomes at 6 and 12 months
 - 2c. The cumulative use of healthcare resources and cost after discharge
- 3) To assess the factors associated with non-adherence to recommended secondary prevention therapies, with special emphasis to socioeconomic factors and gender issues.

4. STUDY DESIGN AND RESEARCH PLAN

4.1. DESIGN.

Prospective, matched cohort study of patients hospitalized for a type 1 AMI with evidence of obstructive coronary artery disease who are discharged home alive. Women will be enrolled first, ideally in a consecutive manner, as they are the focus of the study. Men will be recruited subsequently as the comparison group, with 1:1 matching for age and ECG presentation. Matching will be performed locally, in each study site (hospital). All patients will undergo 1-year follow-up with clinical and therapeutic adherence evaluation.

Reference cohort: 500 women discharged alive after a hospitalization for a type 1 AMI with significant CAD

Comparator cohort: 500 age (± 2 years) and ECG (STEMI/NSTEMI) locally matched men discharged alive after a hospitalization for a type 1 AMI with significant CAD

4.2. RECRUITMENT.

Participant centers

25 hospitals managing routinely AMIs and representing different regions from Spain will be invited to participate

Patient recruitment

All consecutive women fulfilling all inclusion criteria and without exclusion criteria surviving the index hospitalization will be invited to participate. Subsequently, men with inclusion criteria and without exclusion criteria, matched for age and ECG presentation, will be recruited.

Inclusion criteria

- Hospitalization for a type 1 AMI⁶⁹ (detection of a rise and/or fall of cTn value above the 99th percentile URL and with at least one of the followings: symptoms of acute myocardial ischemia; new ischaemic ECG changes; development of pathological Q waves; imaging evidence of new loss of viable myocardium or new regional wall motion

abnormality in a patterns consistent with an ischaemic aetiology; identification of a coronary thrombus by angiography including intracoronary imaging)

- Presence of obstructive coronary artery disease (CAD)⁷⁰ (i.e. coronary artery stenosis $\geq 50\%$)
- Age > 18 years. No maximal age limit applies
- Signed informed consent

Exclusion criteria

- Terminal disease (expected survival < 12 months)
- Unavailable for 12-month follow-up (i.e.: living abroad, social situation...)
- Does not speak Spanish
- Major active comorbidity (severe renal or liver failure, active cancer requiring chemotherapy...), interfering with regular post-MI management

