5.1.2. Disease related factors

AMI features:

- Type of MI (STEMI/NSTEMI)
- Number of diseased vessels
- BARI segment responsible of AMI
- Left ventricular ejection fraction at discharge (LVEF) before discharge (typically by echocardiography)
- Killip class (on admission, “maximal”)
- In-hospital complications (heart failure, bleeding, arrhythmias, cardiogenic shock).

In-hospital management:

- Reperfusion rates and times (for STEMI)
- Patients receiving coronary angiography (for non-STEMI) and time since diagnosis to coronary angiography
- Type of coronary revascularization
- Coronary revascularization rates and completeness
- Admission to the coronary unit
- Length of hospital stay

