6. STATISTICAL ANALYSIS

A minimum sample size of 820 participants (410 per group) was estimated for an expected relative difference in recommendations compliance of the all-or-none composite primary outcome of 20%. An α error of 0.05 and a β error of 0.20 were considered for the sample size. The recommendations compliance was estimated as 42% for women and 52% for men. With the consideration of 20% of lost to follow-up (discontinuations) the total sample size is 984 patients, which is rounded out to 1000 patients (500 women and 500 men). To increase regional representation and allow exploration of potential regional variability, 25 hospitals from all regions in Spain (17 Autonomous Communities) will be invited to participate.

For the description of continuous variables, mean and SD, or median and interquartile range will be used for Gaussian and non-normal distributions, respectively. For describing categorical variables, frequencies and percentages per category will be used. Categorical variables will be compared using the chi² test, whilst continuous variables will be compared using the student *t* test.

Logistic regression models will be used to evaluate differences in binary outcomes between women and men (in hospital AMI management, post discharge MI management). All subjects will be assumed to have a fixed follow-up (12±1 month). Multivariate adjusted models will be used to address any potential confounding in the associations between sex and each of the outcomes. Covariates will be selected based on their pre-defined clinical value and the unbalances observed across groups in the univariate analyses. Linear, multinomial or ordinal regression models would be used in case of continuous, categorical, or ordinal outcomes, respectively.

In addition to the models evaluating the association between sex and outcomes, a predictive model will be conducted to set predictors for the following outcomes:

- 1) a composite of all preventive therapies (all-or-nothing for diet, physical activity, P2Y₁₂ inhibitors, statins, and beta blockers or ACE inhibitors [if prescribed at discharge]), and

- 2) each group of preventive interventions (drugs, cardiac rehab, diet, physical activity)

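### Section 6 models in-hospital management by sex in a cohort of hospital survivors, so the odds ratio does not estimate the sex gap in acute care, and its bias has no known direction

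*Protocol*

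**What the plan says.** Section 4.1 describes a cohort of type 1 AMI patients with obstructive disease "who are discharged home alive". The reference cohort is "500 women discharged alive after a hospitalization for a type 1 AMI with significant CAD"; the male comparator, matched on age and ECG type within each hospital, carries the same survival condition. Section 4.2 repeats it for women: those "surviving the index hospitalization will be invited to participate".

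Section 6 then says that logistic regression will "evaluate differences in binary outcomes between women and men (in hospital AMI management, post discharge MI management"). The same paragraph plans multivariable adjustment for confounding of the association between sex and each outcome.

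The variables concerned are under In-hospital management in Section 5.1.2: reperfusion, angiography, revascularization, coronary unit admission and length of stay. Section 5.1.2 belongs to Section 5.1, Baseline Characteristics. In-hospital management is in none of the hypotheses (Section 2), the specific objectives (Section 3) or the co-primary, secondary and exploratory outcomes (Section 5.3). The general objective is itself limited to a comparison "between women and men surviving a type 1 AMI (with obstructive CAD").

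**The concern.** Selecting on survival to discharge suits outcomes counted from discharge. It does not suit an outcome that occurs before discharge and influences who gets there. Section 1 gives treatments begun in the acute phase part of the credit for falling mortality after AMI, so the protocol itself treats acute care as a cause of survival. A regression of acute management on sex among survivors then conditions on a consequence of the outcome being modelled.

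The protocol also gives reason to suspect that this selection may differ by sex. Section 1 says that women are less likely to be reperfused in time, reports "a higher risk of complications, such as bleeding, cardiogenic shock or mechanical complications", and notes higher in-hospital mortality in young women. Section 6 gives age special attention because of that mortality, yet those deaths cannot enter the cohort.

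What is at stake is one side claim. An adjusted OR for acute management by sex could be read as the acute-care gap in Spanish hospitals, and nothing in the text limits that reading.

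**Working it through.** **Plan's own figure.** The protocol gives none for this comparison. Its sample size of 410 per group concerns adherence (42% v 52%). It reproduces with a two-sided 5% test, 80% power and continuity correction, and has no bearing here.

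**Formula.** Let *p* be the proportion given an acute treatment within one sex, *d_T* the in-hospital mortality if treated and *d_U* the mortality if untreated.

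- Proportion treated among survivors = p(1 − d_T) / [p(1 − d_T) + (1 − p)(1 − d_U)].
- Odds treated among survivors = [p/(1 − p)] × R, where R = (1 − d_T)/(1 − d_U).
- Survivors' sex OR = all-admissions OR × (R in women / R in men).

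The last line gives the direction. If treatment multiplies survival by the same factor in both sexes, the OR does not change. If the factor is larger in women, an OR below 1 moves toward 1. If it is smaller in women, the OR moves further from 1. The identity also holds within strata of age, ECG type or other covariates, so matching and adjustment do not remove the problem.

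**Inputs.** The documents give no treatment rates and no mortality by sex and treatment. All rates below are assumptions chosen to show the range.

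**Illustration A.** Treated: 70% of women, 80% of men. All-admissions OR = (0.70/0.30)/(0.80/0.20) = 0.583; difference −10.0 points. Men's mortality is 4% treated and 12% untreated throughout, so R in men = 0.96/0.88 = 1.091.

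| Women's mortality, treated / untreated | R in women | Survivors' OR | Difference (points) | Effect on OR |
|---|---|---|---|---|
| 4% / 12% | 1.091 | 0.583 | −9.6 | unchanged |
| 6% / 18% | 1.146 | 0.613 | −8.6 | gap shrunk |
| 8% / 24% | 1.211 | 0.647 | −7.5 | gap shrunk |
| 8% / 12% | 1.045 | 0.559 | −10.4 | gap enlarged |
| 10% / 10% | 1.000 | 0.535 | −11.4 | gap enlarged |

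Worked line, 6%/18%: R in women = 0.94/0.82 = 1.146; 0.583 × 1.146/1.091 = 0.613.

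**Illustration B, reperfusion.** Reperfused: 85% of women, 90% of men. All-admissions OR = (0.85/0.15)/(0.90/0.10) = 0.630; difference −5.0 points.

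| Mortality, reperfused / not: women | Men | Survivors' OR | Difference (points) |
|---|---|---|---|
| 7% / 20% | 5% / 15% | 0.655 | −4.1 |
| 6% / 30% | 5% / 20% | 0.712 | −3.1 |
| 6% / 20% | 5% / 20% | 0.623 | −4.5 |
| 7% / 20% | 5% / 20% | 0.616 | −4.6 |

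In the last two rows the OR moves away from 1 while the difference in points still falls. Direction therefore depends on the scale as well as on the mortality pattern. Section 6 specifies logistic regression, so the OR is the relevant scale.

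**The case against.** The strongest defence is reach. Survivors are the right population for adherence, risk-factor control and post-discharge events. The general objective says so openly, and nothing in the protocol claims to estimate acute-care gaps among all admissions. The in-hospital comparison is a few words in one parenthesis, and its variables are filed as baseline characteristics. This stands, and it makes the point a minor one. It does not remove the point, because Section 6 still turns those baseline variables into modelled outcomes, with confounder adjustment and no limit on interpretation.

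A reader might go further and infer that a real gap will be shrunk, perhaps until it seems to have closed. The documents do not support this, for three reasons.

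- **Direction.** The survivors' OR can be unchanged, shrunk or enlarged, and the mortality figures that would decide are not given.
- **Mortality by sex.** Section 1 reports higher in-hospital mortality in women under 45 and a slight rise over time in women. It attributes women's worse prognosis traditionally to older age and comorbidity. It does not show higher mortality in women matched to men on age and ECG type, so a larger loss of women from this cohort cannot be assumed.
- **Complications.** The most dramatic example would be cardiogenic shock, which can itself be fatal. But "In-hospital complications (heart failure, bleeding, arrhythmias, cardiogenic shock") is listed under AMI features in Section 5.1.2, apart from In-hospital management, and Section 6 names only the latter. Large distortions computed for shock do not carry over to the planned comparison.

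**Conclusion.** The structural problem is real. A regression of in-hospital management on sex, fitted only in people discharged alive, does not estimate the sex difference in acute care, and no other part of the protocol repairs this. Matching balances age and ECG type among survivors, and adjustment works on survivors; neither brings back the deaths.

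The size is unknown and the sign is not determined. Under the assumed rates the distortion is modest: an OR of 0.583 becomes 0.535 to 0.647, and an OR of 0.630 becomes 0.616 to 0.712. These ranges rest entirely on assumed treatment and mortality rates and are not forecasts for this study.

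The co-primary endpoints, the other listed outcomes and all stated objectives are untouched. The correction is worth making because it limits what may be concluded, at almost no cost.

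**What to change.** In Section 6, remove in-hospital AMI management from the binary outcomes modelled by sex. Present those variables by sex as baseline descriptors of survivors, as Section 5.1.2 already files them, and add that no sex difference in acute care will be inferred.

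The cost is one sentence, plus one side claim that the design cannot support.

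Counting in-hospital deaths by sex is not a ready substitute. Section 7 mentions screening logs only for recording file names and locations, and men are approached only as matches for enrolled women. Such a count would need data collection that the protocol does not describe.
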